## Background

IBS, characterized by abdominal pain and abnormal bowel habits, but normal findings at clinical investigations, is the most common functional GI disorder, and affects 5-10% of the adult population. Few effective treatment alternatives exist, largely due to incomplete understanding of the underlying pathophysiology. Many IBS patients frequently consult different health care providers, report absence from work, and have poor quality of life, leading to profound suffering, and high costs for individuals and society.

Current view on IBS pathophysiology. Today, IBS is considered a disorder of gut-brain interactions, where abnormalities in the gut and the brain interact and explain the hallmark symptoms of IBS, abdominal pain and abnormal bowel habits. However, causes of the abnormal function in the gut and the disturbed interaction with the brain are unknown.

The gut microenvironment and food. Gut microbiota alterations, as well as other factors in the gut microenvironment, such as altered immune and barrier function, are considered to be of relevance in IBS. The current view is that these alterations can interact with our nervous system and generate symptoms in susceptible individuals. However, the exact mechanisms are still not known. To date, the most important factors accepted to trigger the onset or exacerbation of IBS are gastrointestinal infections and psychological factors. In addition, the majority of patients report food-related symptoms. The focus on diet and IBS has so far mainly been on major food groups (e.g., fermentable carbohydrates), rather than on individual nutritional components and potential allergy-resembling mechanisms. However, recent ground-breaking studies indicate that diet-microbiota interactions are responsible for local immune reactions in the gut. A study in mice demonstrated that a bacterial GI infection could promote break of oral tolerance to dietary antigens, and ingestion of these food antigens after the infection was resolved led to mast cell activation and the development of long-standing visceral hypersensitivity. Moreover, local injection of food antigens into the colon in a small group of IBS patients induced local edema and mast cell activation, supporting the involvement of loss of tolerance to dietary antigens in IBS. Another study identified signs of nonclassical food allergy in the small intestine in more than 50% of patients with IBS. These studies have demonstrated novel peripheral mechanisms underlying food-induced symptoms in IBS without systemic signs of classical allergy, induced by diet-microbiota interactions.

This project will focus on the recent discoveries of *Brachyspira* infection and intestinal allergy-like immune reactions as potential causative factors for symptoms in IBS. It will advance this field substantially, by identifying novel mechanisms for symptom generation and treatment targets for large groups of patients, and specifically identify subgroups of IBS patients where treatment options today are absent. To achieve the goals, we will use our unique collaborative set-up with large and well-characterized patient cohorts and state-of-the art methods to study the link between symptom reports and objective findings and test novel treatment options

## Aim

To define local immune responses in the GI tract to food antigens in IBS patients with and without *Brachyspira* infection using advanced imaging.

## Hypothesis

We hypothesize that *Brachyspira* infection can cause IBS symptoms by inducing loss of oral tolerance to dietary antigens through development of food-specific intestinal immune reactions and subsequent development of visceral hypersensitivity.

## Methods

### Subjects

All patients will be carefully characterized at baseline including detailed clinical phenotyping, allergy testing, nutrient intake, detailed information about adverse food reactions, collection of blood and fecal samples, and identification of *Brachyspira* in colonic biopsies. Before and after the endoscopic food challenge, biopsies will be taken. These will be analyzed with a particular focus on the mucosal immune response (e.g. tryptase activity, as a measure of mast cell degranulation; immunohistochemistry to determine IgE/mast cells and other immune cells; mucosal structure, eosinophils, and intraepithelial lymphocytes with Hematoxylin and Eosin histology). Baseline characteristics (e.g. clinical and nutritional profile, gut microbiota composition and function, *Brachyspira* infection, immune activation) associated with a positive food challenge test, i.e. with an intestinal allergy-like reaction, will be determined.

### Inclusion criteria

- IBS patients aged between 18 and 70 years.
- Patients with IBS diagnosis according to their treating physician.
- Association between intake of food and GI symptoms.
- Witnessed written informed consent prior to any study procedures.
- Patients who are capable to understand the study and the questionnaires, and to comply with the study requirements.

### Exclusion criteria

- Patients with relevant concurrent organic GI disease (inflammatory bowel disease, abdominal cancer), or a major disease such as diabetes, uncontrolled thyroid disease, heart disease, kidney disease, liver disease, and active malignant disease (not those that were in remission at least 5 years).
- Patients with a history of bowel surgery (not appendectomy or cholecystectomy) that affects GI motility.
- Patients with systemic food allergy as evidenced by positive allergy tests (blood, prick test).
- Clinical history of severe allergic reactions.
- Patients with concurrent major confounding condition(s) based on the clinician's judgement, e.g. DOMINANT psychiatric disorder, vital depression, alcohol or substance abuse in the last 2 years.
- Female patients who are pregnant or lactating (females of fertile age are requested to use a safe contraceptive) at the time of inclusion.
- Patients who use or used new medications that affect the GI functioning within 1 month before the start of the study.

### Questionnaires

- Baseline questionnaires; demographic, symptoms, symptom/medication/diet history, co-morbid medical conditions
- IBS symptoms: IBS-Symptom Severity Scale (IBS-SSS) and Gastrointestinal Symptom Rating Scale (GSRS)-IBS
- Psychological distress: Hospital Anxiety and Depression Scale (HADS), Patient Health Questionnaire (PHQ)-9 (both visit 1,4,5,6, generalized Anxiety Disorder 7-item scale (GAD-7)
- Somatization: PHQ-15 for the number and severity of bodily symptoms.
- Gastrointestinal specific anxiety: Visceral Sensitivity Index (VSI).
- Sensitivity: Central Sensitization Inventory (CSI).
- Food avoidance and restriction: (ARFID).

- Stool habits and GI symptoms: 14-day GI symptom diary based on Bristol Stool Form Scale (BSFS).
- Quality of life: IBS-Quality of Life (QOL).
- Food intake: 4-days food diary, MealQ.

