## Study visits

### **Visit 1 – screening visit – 2 hours**

1. Screening. The subjects come fasting (8 hours) to our lab and the researcher obtains informed consent, confirms the IBS diagnosis and study criteria. Clinical routine blood tests for diagnostic purposes (blood cell count, liver, kidney, thyroid gland status, electrolytes, fasting glucose, C-reactive protein, transglutaminase (gluten) antibodies, and faecal calprotectin. The subjects fill in the baseline questionnaires. Height and weight are measured.

2. Rectal barostat. The researcher explains the rectal barostat procedure and the subjects undergo the rectal barostat. Thereafter, they will obtain information about the screening period including questionnaires, tubes for fecal and urine samples. Visit 2 and 3 will be planned.

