**Visit 4-6: only if COLAP or CLE were positive for 1 or more food items.**

### **Visit 4**

Questionnaires (IBS-SSS, GSRS-IBS, HAD, PHQ-15). Instructions and advice from the dietician which food item(s) to exclude from the diet, based on CLE or COLAP. Period of exclusion: 4 weeks.

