### **Visit 5 (digital, 4 weeks after visit 4)**

Questionnaires (IBS-SSS, GSRS-IBS, HAD, PHQ-15). Instruction to re-introduce the CLE or COLAP positive food item(s) for 4 weeks.

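### Does the mismatch between PHQ-9 and PHQ-15 at visits 4 to 6 put any result of the study at risk?

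*Protocol*

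**What the plan says.** Under the heading Questionnaires, the psychological distress entry reads in part: "Hospital Anxiety and Depression Scale (HADS), Patient Health Questionnaire (PHQ)-9 (both visit 1,4,5,6". The bracket is never closed, and GAD-7 follows after the visit numbers. These are the only visit numbers in that section. A separate entry reads "Somatization: PHQ-15 for the number and severity of bodily symptoms" and gives no visits.

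The description of Visit 1 says only "The subjects fill in the baseline questionnaires". The first entry of the Questionnaires section describes baseline questionnaires by content (demographics, symptoms, history, co-morbidity) and does not name HADS, PHQ-9 or PHQ-15.

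The later visits are conditional: "Visit 4-6: only if COLAP or CLE were positive for 1 or more food items". Visit 4 begins "Questionnaires (IBS-SSS, GSRS-IBS, HAD, PHQ-15). Instructions and advice from the dietician which food item(s) to exclude from the diet". Visit 5 begins "Questionnaires (IBS-SSS, GSRS-IBS, HAD, PHQ-15). Instruction to re-introduce the CLE or COLAP positive food item(s) for 4 weeks". Visit 6 consists of the same four-instrument list. PHQ-9 is on none of these lists and is not named anywhere outside the Questionnaires section.

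**The concern.** The protocol gives two different instructions for the same visits. Someone building the case report form from the Questionnaires section would include PHQ-9 at visits 4, 5 and 6. Someone working from the visit descriptions would leave it out and collect PHQ-15 instead. The two cannot be read as one instrument under two names, because the Questionnaires section places PHQ-9 under psychological distress and PHQ-15 under somatization.

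These visits frame the dietary part of the study: before exclusion, after four weeks of exclusion, and after four weeks of reintroduction. A self-report of a patient's state at such a visit cannot be recovered later. If PHQ-9 was meant to be followed through that sequence, the visit lists would lead staff to miss it in every test-positive patient.

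**Working it through.** No arithmetic applies beyond a count, and the protocol states no figure to reproduce. The check sets the two places side by side.

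| Instrument | Visits 4, 5, 6 per Questionnaires section | On the lists for visits 4, 5, 6 |
|---|---|---|
| HADS | all three | 3 of 3 (as HAD) |
| PHQ-9 | all three | 0 of 3 |
| PHQ-15 | no visits given | 3 of 3 |
| IBS-SSS | no visits given | 3 of 3 |
| GSRS-IBS | no visits given | 3 of 3 |

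**Is the mismatch real?** Yes. The word 'both' comes straight after HADS and PHQ-9, so the natural reading schedules those two. The lists for visits 4 to 6 are complete running text, show no redaction, and are not worded as examples.

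**Which side is the slip?** The protocol does not say. Two readings are open.

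1. PHQ-9 was left off the visit lists. Then PHQ-9 is missed at three visits per test-positive patient if staff follow the lists.
2. The visit numbers were meant for HADS and PHQ-15. The lists pair exactly these two at all three visits, and the distress entry is visibly unedited, with its open bracket. Then nothing intended is missed at visits 4 to 6, and the only error is in the wording of the Questionnaires section.

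Any count of omitted PHQ-9 forms presupposes the first reading. It also counts one discrepancy three times, because the three lists are identical.

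**What depends on PHQ-9?** The Aim concerns local immune responses to food antigens in patients with and without *Brachyspira*. The Hypothesis concerns loss of oral tolerance and visceral hypersensitivity. The Subjects section names baseline characteristics to be related to a positive challenge, and all of them precede visit 4. The inclusion and exclusion criteria do not use PHQ-9. Entry to visits 4 to 6 depends on the challenge result alone. So PHQ-9 at visits 4 to 6 feeds no stated analysis or decision.

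**What remains if PHQ-9 is not collected there?** HADS remains at all three visits, and the protocol groups it with PHQ-9 under psychological distress. The two IBS symptom scales, IBS-SSS and GSRS-IBS, are also on all three lists and are untouched by the discrepancy.

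**Visit 1.** The Visit 1 text names no instruments. Read literally, the baseline entry in the Questionnaires section covers demographics, symptoms, history and co-morbidity rather than the distress scales. The term may be used loosely, so this neither confirms nor refutes collection of PHQ-9 at visit 1, and it establishes no second contradiction.

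**The case for a change.** The strongest argument for acting is that the contradiction is certain, the correction is almost free, and missed responses are lost for good. A correction would need either a change of wording in the Questionnaires section or one additional 9-item form at three visits, two of them digital. The protocol is also the right place to fix which form is given at which visit, so the point cannot be passed to a statistical analysis plan.

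Most of this stands. The texts do disagree, and a study team that notices will want to tidy them. What does not stand is the step from inconsistency to harm. Loss of intended data at visits 4 to 6 occurs under only one of the two open readings. Even then, the lost item is a second distress measure, in a conditional subgroup, that no stated aim or decision uses. A low cost of correction does not show that anything is gained in the results.

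**Conclusion.** The inconsistency is real, but it is clerical and calls for no change to the plan. PHQ-9 is on 0 of 3 follow-up lists against a schedule that names it for all three. Whichever version staff follow, HADS and both IBS symptom scales are collected before exclusion, after exclusion and after reintroduction, and the study's stated questions are answered from the same data.

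This conclusion rests on two points. First, PHQ-9 has no role beyond its single mention in the Questionnaires section, which holds for the protocol as it stands. A statistical analysis plan that made PHQ-9 change an outcome would alter the weight of the point, but none is at hand. Second, HADS is in fact given at visits 4 to 6, as both places in the protocol say. The protocol does not show which side is the slip, nor whether data collection has begun, and the conclusion depends on neither.

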## Measurements/tests

### Colonoscopic allergen provocation test, COLAP:

- A local allergen provocation test, where dietary antigens (soy, wheat, egg, gluten and milk), with saline and histamine as negative and positive controls, respectively are injected in the sigmoid mucosa (similar to skin prick test used for clinical allergy testing).
- The intestinal reaction is determined visually (“wheal and flare reaction”), and biopsies are taken to characterize the immune response.
- Bowel preparation before the investigation follows the normal clinical routine for colonoscopy, and i.v. sedatives and opioids are given during the investigation according to clinical routines at the endoscopy unit

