### **Visit 2 – Sigmoidoscopy – 2 hours**

1. Blood test, microbiota, immunological markers and metabolites. The subjects come fasting (8 hours) to our lab, where a nurse will take fasting blood samples (20 ml). The researcher will freeze fecal (10g), urine (3ml) and serum (5ml) samples in minus 80 degrees for later analyses. Pregnancy test (urine) is taken.

2. Questionnaires. The researcher checks the filled in questionnaires (screening period) and the subjects fill in the web-based questionnaires.

3. Sigmoidoscopy. The researcher and gastroenterologist explain the procedure. No bowel preparation, fresh biopsies will be taken for specific analyses and biopsies will be stored (a.o. -80 degrees Celsius) for subsequent analyses.

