### **Visit 3 – CLE or COLAP test – 5 hours**

1. Blood test, microbiota, immunological markers and metabolites. The subjects come fasting (8 hours: CLE , or according to laxatives protocol: COLAP) to our lab. The researcher will freeze fecal (10g) samples in minus 80 degrees for later analyses.

2. A) CLE. The researcher and gastroenterologist explain the procedure. Check if patient complied with dietary guidelines. The subjects undergo the CLE. Biopsies will be frozen. B) COLAP. The researcher and gastroenterologist explain the procedure. Check if patient complied with bowel preparation and dietary guidelines. The subjects undergo the COLAP. Biopsies will be frozen.

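### The COLAP reaction is read by eye, and the protocol does not provide for hiding from the reader which site holds which food or control

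*Protocol*

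**What the plan says.** The protocol's COLAP section lists five antigens (soy, wheat, egg, gluten, milk), with saline as negative and histamine as positive control. For the readout it states that "The intestinal reaction is determined visually" as a wheal and flare reaction, and that "biopsies are taken to characterize the immune response". It names no reader and says nothing on whether the reader knows what each site contains.

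The Visit 3 section, which covers conduct on the day, adds that "The researcher and gastroenterologist explain the procedure", that preparation and diet are checked, and then: "The subjects undergo the COLAP. Biopsies will be frozen". It does not mention coding, site order or independent reading.

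The result is used in two places:

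- Under Subjects, baseline characteristics "associated with a positive food challenge test, i.e. with an intestinal allergy-like reaction, will be determined".
- Visits 4 to 6 take place "only if COLAP or CLE were positive for 1 or more food items". At Visit 4 the dietician's advice on what to exclude follows the CLE or COLAP result, and at Visit 5 the same foods are re-introduced.

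At baseline the protocol also collects "detailed information about adverse food reactions".

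**The concern.** A wheal and flare judged by eye leaves room for discretion, more so because the COLAP section gives no size threshold against saline or histamine. If the reader knows that a given site holds, say, wheat, a borderline reaction can be called differently than it would be at an unlabelled site. Patients enter because they link food with symptoms, and their food reactions are recorded before the test, so information that could create such an expectation exists in the study.

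Two results would be exposed. The association between baseline profile and a positive test could become partly circular if calls drift towards foods that patients already suspect. The exclusion and re-introduction periods would then partly test the patient's own suspicion instead of an allergy-like reaction. Neither can be repaired at analysis, because patients and foods have by then been selected on the call.

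**Working it through.** **1. Is masking provided for anywhere?** I looked for coded syringes, random position, a masked scorer or independent reading under Subjects, Measurements/tests and each Study visit. None appears. No section says that reading is open either.

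**2. Do the existing safeguards do the same job?** The saline and histamine sites anchor the reading within each patient, but they do not hide which site holds which food. Biopsies could later show whether visual calls and tissue findings agree. Their stated purpose is to characterize the immune response, and at Visit 3 they are frozen. The protocol neither makes them part of the positive call nor excludes them from it.

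**3. Illustration of size.** The protocol gives no reader error rate, sample size or power, so there is no figure to reproduce. From the protocol I take 5 foods and the rule of one or more positive foods. Everything else is assumed:

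- false-positive rate per food site 5% without expectation;
- rate *b* at the *m* foods the reader expects to be positive;
- the patient has no true reaction to any food;
- sites independent, unless stated otherwise.

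The share of such patients called positive is 1 − (1 − *b*)^*m* × 0.95^(5 − *m*).

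- No expectation: 1 − 0.95^5 = 1 − 0.7738 = 22.6%.
- *b* = 10%, *m* = 1: 1 − 0.90 × 0.8145 = 26.7%, an increase of 4.1 points.
- *b* = 10%, *m* = 2: 1 − 0.81 × 0.8574 = 30.6%, an increase of 7.9 points.

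| Assumed *b* | Increase, one food | Increase, two foods |
|---|---|---|
| 7.5% | 2.0 points | 4.0 points |
| 10% | 4.1 points | 7.9 points |
| 15% | 8.1 points | 15.4 points |

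The 22.6% comes from testing five foods and would apply to a masked reader too. Only the increases belong to this point. If sites are correlated (Gaussian copula, latent correlation 0.5, *b* = 10%), the increases are 3.1 and 5.8 points.

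**4. Which foods the false calls fall on.** The expected share of false-positive site calls that fall on expected foods is *mb* / (*mb* + (5 − *m*) × 0.05). This does not depend on independence.

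- One food: from 0.05/0.25 = 20.0% to 0.10/0.30 = 33.3% as *b* goes from 5% to 10%.
- Two foods: from 0.10/0.25 = 40.0% to 0.20/0.35 = 57.1%.

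Under these assumptions, the choice of food shifts more than the number of patients called positive.

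**The case against.** The strongest reply is that this is silence and not error. The COLAP section is a short summary, and coding may simply lie below its level of detail. Within-patient controls are a real safeguard, and every rate above is assumed. Most of this stands: the point is an unprotected risk, not demonstrated bias. It does not remove the point, because masking must be in place when the sites are read and no later analysis plan can supply it.

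A reader might infer more than the documents support:

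- *That COLAP is read unmasked.* The protocol does not say so.
- *That a positive test means the visual call alone.* The Subjects section speaks of a positive food challenge test and also plans biopsies before and after challenge. No interval between Visits 3 and 4 is fixed, so freezing the samples does not show that tissue results come too late to count.
- *That staff demonstrably know each patient's suspected foods.* At Visit 2, "The researcher checks the filled in questionnaires", but those from the screening period are the food diary, the GI diary, IBS-SSS and GSRS-IBS. That check does not establish knowledge of trigger foods, and no section says that the gastroenterologist sees them.
- *That the comparison by Brachyspira status is biased.* Drift towards expected foods distorts it only if the drift differs by infection status. The protocol does not say whether that status is known by Visit 3.
- *That food history must be kept from the gastroenterologist.* Once site contents are coded, knowing which foods a patient suspects gives little means of favouring a particular site.

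The CLE section is also silent on masking, and CLE feeds the same rule for Visits 4 to 6. The point is confined to COLAP because that is where the protocol itself calls the reading visual. Calls made on CLE are not protected by the fix below.

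**Conclusion.** The point holds as a cheap improvement. COLAP is judged visually, nothing in the protocol keeps the reader unaware of site contents, and the result contributes to the baseline association, to entry into Visits 4 to 6 and to the choice of excluded foods. Expectation could shift which foods are called positive.

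The documents do not allow the size to be estimated. The increases of 2.0 to 15.4 points are illustrations under assumed error rates. They apply only to patients with no true reaction, whose share of the cohort is unknown, so the effect over all patients would be smaller by an unknown factor. If biopsy findings do form part of the positive call, the exposure would be smaller again.

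**What to change.** Add to the COLAP section that:

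1. the five antigens and both controls are given from coded syringes, prepared by a team member who does not score the reactions;
2. the order of sites is random for each patient, controls included;
3. each site is scored against that patient's own saline site, and the score is recorded before the code is opened;
4. the code is available at once if needed for safety.

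No change is needed to the clinical history that the gastroenterologist may see.

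The cost is protocol wording, an allocation list, coded syringes and a few minutes of preparation per session. There is no extra visit or procedure. The Visit 3 section already names a researcher and a gastroenterologist, so the preparing and scoring roles can be separated without new staff, provided the one who prepares the syringes does not score. One limitation remains: the histamine site may still be recognisable from its reaction, so masking protects mainly the five foods and saline.
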